4.6 Stopping Rules

Individuals: Aerosolization will require the usual bedside monitoring by NICU devices and personnel appropriate for all patients in the first hours of life with significant respiratory difficulty. Any patient, who in the judgment of the clinical care team, is experiencing an adverse event due to the aerosolization will have it stopped and not restarted. Taking appropriate remedial steps to resolve an adverse event will be the responsibility of the patient’s clinical care team. The patient will not receive additional aerosol therapy if dosing is discontinued due to an adverse event.

Sites. Following an adverse event resulting in discontinuation of aerosol therapy, recruitment by that site will automatically be suspended.

The Principal Investigator (or a co-investigator) will notify the sponsor within 24 hours of the adverse event. The Sponsor will notify the Study Chair and the Chair of the Data Monitoring and Safety Committee (DMSC) within 24 hours of receiving notification.

The site will not re-start recruiting to the study until the site P.I., the Study Chair and the Sponsor decide that appropriate remediation, if necessary, has been achieved.

Any adverse event during aerosolization will be reviewed by the NICU Medical Director at the site within 24 hours of occurrence. S(he) shall contact and consult with the Study Site P.I. and after that review either allow the study to continue recruiting or suspend the study. In either case the local IRB and the Medical Director of the Sponsor will be notified within 24 hours. If the study is suspended it will not be restarted until the NICU medical director, the site P.I., the local IRB, and the Sponsor have all approved the decision to restart the trial at that site.

In addition, if the study is suspended at any one site the Sponsor will notify the P.I. at all other participating sites and the national and all local IRBs. Any local IRB, site P.I. or the Sponsor can suspend the study at any or all of the other participating sites. If suspended at other sites restarting will require prior approval by the local IRB and P.I. and the Sponsor.

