Entire Trial: The Study Chairman, the DSMB chair and the Sponsor will confer upon receiving notification of any adverse event resulting in discontinuation of aerosol therapy with 24 hours. If any one of the three judges that the welfare of patients is best served by suspending recruitment to the trial the Sponsor shall immediately notify all the sites that recruitment for the study has been suspended and the reason for the suspension.

Within 5 days the Principal Investigator of the site where the adverse event occurred will submit a full description of the adverse event along with relevant data from the patient's medical record. The PI will provide an assessment and recommendations with the summary and the data.

Upon receipt of report from the site PI the Study Chair and the DMSC shall separately review the communication from the site P.I. The Study Chair and the Chair of the DMSC will hold a teleconference to reach a consensus to advise the Sponsor to:

- (a) Stop the trial for the safety of patients.
- (b) Suspend the trial until the cause of the adverse event is identified and remedied.
- (c) Suspend the trial at the site of the adverse event only until a cause is remedied.
- (d) Restart the trial at the site and continue the trial at the other sites.

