8. ASSESSMENT OF SAFETY

8.1 Parameters

Adverse Events During Aerosolization.

- 1) Discontinuation of aerosolization before the full dose is given for any reason
- 2) Incidence, magnitude and duration of adverse cardiopulmonary effects:
 - (A) Hypoxemia defined as O₂ saturation of < 80 % for >1 minute despite interventions.
 - (B) Airway obstruction defined as blockage of ventilation for >1 minute producing hypoxemia and bradycardia and requiring endotracheal suctioning and/or re-intubation.
 - (a) during Infasurf aerosolization(s)
 - (b) during instillation(s)
 - (C) Other.

Other safety parameters: These data will be extracted from the medical record of each patient from birth to 28 days of life, death or discharge (whichever is first).

- 1) Incidence of pneumonia, sepsis or other major infection to 28 days
- 2) Incidence and severity of seizures, brain hemorrhages or other brain injuries
- 3) Incidence and severity of necrotizing enterocolitis
- 4) incidence and severity of bronchopulmonary dysplasia.
- 5) Incidence and severity of any other severe unexpected adverse events.

8.2 Methods Identification of all safety outcomes will be by review of the patient’s medical record.

8.3 Analysis Severe, unexpected adverse events. Any severe, unexpected adverse event occurring to aerosolized assigned patients will be immediately reported to the medical director of a participating site. The medical director will review the adverse event and determine if it is related, or possibly related, to the administration of aerosolized Infasurf. If the event is considered “related” or “possibly related” the sponsor will be immediately notified and will be responsible for filing the appropriate notification to FDA. The sponsor will provide the same information to the study chair and to the other study sites. The local site P.I. will be responsible for providing the local IRB with the information about the event.

Non-serious adverse events By regulation an “adverse event means any untoward medical occurrence associated with the use of a drug in humans, whether or not considered drug related.” (21 CFR 312.32(a)).

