Randomization: Subjects will be randomized to the intervention or active control arm in a 1:1 fashion using a stratified permuted block randomization scheme with variable block sizes of 2 and 4. Randomization lists will be generated by the study biostatistician which will then be used to create an envelope-based system to be used at the individual study sites. Subjects will be included in primary data analyses according to their randomized assignment irrespective of the treatment actually received (intent-to-treat). Exceptions would include those who withdraw their consent to use any of their data prior to subject evaluation.

Accrual. Subjects will be accrued to the study on a first-come basis. The projected accrual is approximately 80 per month, and therefore recruitment is expected to be complete at most 365 days following the study starting point. Subjects will be followed to hospital discharge or 28 days whichever is shorter so total study duration will be approximately 13 months.

Descriptive analyses. Measured outcome variables will be summarized overall and by relevant demographic and baseline variables. Descriptive statistics such as frequencies and relative frequencies will be computed for all categorical variables. Numeric variables will be summarized using simple descriptive statistics such as the mean, standard deviation and range. A variety of graphical techniques will also be used to display data, ex. histograms, boxplots, scatterplots, etc.

Primary efficacy analyses. The primary efficacy analysis will be performed within each cohort separately and is based on a test for superiority of the experimental treatment relative to active control with regards to intubation rate. An overall assessment of the probability of intubation differences across study sites will be done using the Cochran-Mantel-Haenszel test. A one-sided nominal significance level of 5% will be utilized. Additional analyses will be performed utilizing both cohorts of subjects in order to assess differential treatment effects.

Primary safety analyses. All adverse events will be recorded during the study period and then tabulated at the end of the study.

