9.3 Criteria for trial termination

There will be no termination of the trial for early efficacy. Criteria for termination for futility are presented in 9.1 in interim analysis. The data monitoring and safety committee will review the adverse events and will recommend to the study chair and the sponsor that the trial be suspended or discontinued for safety. Since this is a study of an alternative

method of administration of Infasurf which is FDA approved as safe and effective termination for adverse events unrelated to administration of the aerosol is not included.

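### Sections 4.6, 8.3 and 9.3 do not join: a death or severe related event after a completed aerosol dose has no prompt, defined route to the safety committee

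*Combined protocol and SAP*

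**What the plan says.** Section 4.6 sets out three linked steps, all with the same trigger.

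- Site: "Following an adverse event resulting in discontinuation of aerosol therapy, recruitment by that site will automatically be suspended".
- Notice: the site informs the sponsor within 24 hours, and then "The Sponsor will notify the Study Chair and the Chair of the Data Monitoring and Safety Committee (DMSC) within 24 hours of receiving notification".
- Trial: the study chair, the committee chair and the sponsor "will confer upon receiving notification of any adverse event resulting in discontinuation of aerosol therapy". Any one of the three can bring about a suspension of recruitment. A site report is due within 5 days. The committee and the study chair review it separately, and the two chairs then advise the sponsor on one of four options, (a) to (d), from stopping the trial to restarting it.

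Section 4.6 also has a broader site rule: "Any adverse event during aerosolization will be reviewed by the NICU Medical Director at the site within 24 hours of occurrence". The local IRB and the sponsor's medical director are told of the outcome. If a site is suspended, "Any local IRB, site P.I. or the Sponsor can suspend the study at any or all of the other participating sites".

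Section 8.3 deals with severe, unexpected events in infants assigned to aerosol, with no limit on timing. The site's medical director judges relatedness. If the event is related or possibly related, the sponsor is told and notifies FDA, and "The sponsor will provide the same information to the study chair and to the other study sites". The site investigator informs the local IRB.

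Section 9.3 gives the committee a general role: "The data monitoring and safety committee will review the adverse events and will recommend to the study chair and the sponsor" suspension or discontinuation for safety. Section 9.1 says of the safety data: "All adverse events will be recorded during the study period and then tabulated at the end of the study".

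**The concern.** The prompt review in 4.6 depends on whether a dose was stopped, not on how grave the event was. Several of the outcomes that the protocol collects can arise after the aerosol has ended: air leak and pulmonary hemorrhage are followed to 7 days (7.2), and brain hemorrhage and other severe events to 28 days, death or discharge (8.1). For these, the plan does not say when or how the committee learns of the event, or who must decide whether recruitment continues.

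At stake is independent oversight. In 4.6 the committee chair is one of three parties who can each cause a suspension. For an event after dosing, 8.3 informs the other two, the sponsor and the study chair, and leaves the committee chair out. This matters more in an unmasked trial in which the sponsor or its designee also manages and analyzes the data (9.1). Infants could go on being randomized to aerosol after a related death without the committee having been asked for a view.

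**Working it through.** No figure in the plan is in dispute, so the check is to set the routes side by side and pass example events through them.

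| Route | Trigger | Covers events after a completed dose? | Committee named? | Decision step attached |
|---|---|---|---|---|
| 4.6 suspension, notice, conference | Event that discontinues aerosol therapy | Not on the plain reading | Yes | Automatic site suspension; conference; options (a) to (d) |
| 4.6 review by the site's medical director | Any event during aerosolization | No | No | Site may be suspended, and then other sites |
| 8.3 | Severe, unexpected event, aerosol arm, judged related or possibly related | Yes | No | None stated |
| 9.3 | None stated | Yes, unless unrelated to giving the aerosol | Yes | Recommendation; no timetable |

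Three illustrative events, not taken from the documents:

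1. A desaturation leads staff to stop a dose. The first row applies. The site is suspended, and the committee chair hears within 24 h (site to sponsor) + 24 h (sponsor to chair) = 48 h at most. The conference, the 5-day report and the choice among (a) to (d) follow.
2. A fatal pulmonary hemorrhage occurs two hours after a completed dose and is judged related and unexpected. Nothing was discontinued and the aerosol was not running, so neither 4.6 route starts. Section 8.3 informs its five recipients. The committee is not among them, and no conference follows.
3. The same event is judged expected, which is possible because pulmonary hemorrhage is a prespecified outcome in 4.1 and 7.2. It now falls outside 8.3 as well. Only 9.3 is left.

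Could the committee receive events 2 and 3 by a scheduled route? Section 9.1 plans board review of interim results at about 1/3 and 2/3 of evaluable subjects. Those looks are described as futility assessments based on conditional power, and no adverse-event listing is mentioned. The only tabulation of adverse events that is described comes at the end of the study. Section 9.3 gives the committee authority over events 2 and 3, but no passage says what brings them to it, or when.

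**The case against.** The strongest reply is 9.3. It gives the committee a review of adverse events that is not confined to those that stop a dose, with power to recommend suspension. It excludes only events unrelated to giving the aerosol, so a related death is in scope. This stands. A reader might infer that events after dosing never reach the committee, and the documents do not support that. Likewise, tabulation at the end of the study does not mean that committee review must wait until then. What is missing is a prompt, defined route.

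Second, a reader might infer that the trial can be paused only if staff stop a dose. That is also too strong. Any event during aerosolization may lead to suspension at the site and then at others. Nor is the trial-wide step an automatic pause: it is a conference at which a party may call for one. Both corrections stand, but neither helps with an event after the dose.

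Third, the trigger may be wider than it looks. Up to three treatments are allowed, and cancelling later ones after an event could count as discontinuing therapy. Section 8.1, by contrast, speaks of stopping before the full dose is given. The ambiguity is real. Even on the wide reading, an infant who has had all three treatments, or who has no indication for another, has nothing left to discontinue.

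Fourth, the rule follows the hazard named in 2.3, interference with breathing during administration, and 9.3 argues that the drug itself is already approved. Severe, unexpected, related events do reach the sponsor, FDA, the study chair and all sites. This explains the emphasis on the dosing period. It does not explain why the committee is left out of 8.3.

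**Conclusion.** The point stands as a gap between 4.6, 8.3 and 9.3. If the plan is followed exactly, a related death or severe event after a completed dose leads to no deadline for informing the committee, no conference and no recorded decision to continue. Only an untimed review applies, and if the event is judged expected, even the 8.3 notices do not go out.

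The size cannot be put as a number. The documents give no rate of severe events after dosing. A reader might compare the minutes of aerosol with the 28-day window, or count the infants enrolled before the first interim look, and treat either as a measure of risk. Neither is one. Infant weights are not given, follow-up ends at discharge, and a share of time is not a share of events. Enrolment is stated as a maximum for two cohorts that are analyzed as separate trials.

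Two assumptions matter. The committee is named in different ways (DMSC, DSMB, Data and Safety Monitoring Board), and these are taken to be one body. Discontinuation of aerosol therapy is read mainly as stopping administration; the wider reading narrows the gap but does not close it.

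**What to change.** Reconcile the three sections with two additions.

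- In 8.3, add the committee chair to those informed, within the 24 hours that 4.6 already uses.
- In 4.6 (Entire Trial), state that the existing conference and options (a) to (d) also apply to any death or severe adverse event judged related or possibly related to the aerosol, whether or not it was expected and whether or not a dose was discontinued.

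The second addition must not depend on an event having been reported under 8.3. That section is limited to unexpected events and could miss a pulmonary hemorrhage judged expected. The site's relatedness judgment and the 4.6 notice to the sponsor and the chairs therefore need to cover these events too. Section 9.3 can then refer to 4.6 and 8.3 for how events reach the committee between scheduled looks.

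This adds a review step. It creates no automatic trial-wide halt and leaves patient care unchanged. The cost is a few sentences of protocol text and a few extra conferences, with no new visits or data collection.

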4.7 Infasurf + Solarys Accounting

Infasurf used in this trial will be identical to current FDA approved Infasurf but provided in a larger vial. Storage of the product will require refrigeration but not masking of product identity. The vials will have a label that allows the study number of the patient (determined by the randomization assignment) and the data of administration to be entered at use.

The Solarys aerosolization device modified for delivery to non-intubated premature infants will be provided packaged with the Infasurf. Each unit will have a label on its packaging with a unique ID number and a space for entering the date and patient ID number when used.

Used vials and devices will be retained after administration by each site and returned to the Sponsor. Unused vial-device units will be returned to the Sponsor at the end of the trial. Reconciliation of vial-device units will be done by the Sponsor.

4.8 Randomization Codes

Each participating site will be provided a separate sequential randomization code in opaque envelopes. The blocks will be small but the size of the blocks will be confidential so investigators cannot predict assignment. Patient assignment will be to the study arm indicated by the next envelope in sequence opened after consent is obtained. The study sponsor will generate the randomization code for each site using the Moses-Oakford algorithm.⁶

4.9 Data Sources

All data will be extracted from the medical record. At the time of administration an entry will be made into the progress notes of all patients who received aerosol that includes the information required to complete the form in Appendix A. This protocol requires no study specific evaluation, testing or monitoring of the patients.

5. SELECTION AND WITHDRAWAL OF SUBJECTS

5.1 Inclusion criteria

Cohort 1: RDS Patients Who Did Not Have Early Surfactant Instillation

- 1) NICU patient, ≥ 1 hour of age and < 12 hours of age.
- 2) Clinical diagnosis of RDS, with or without chest X-ray data.
- 3) Inspired oxygen $\geq 25\%$ and $\leq 40\%$ to maintain adequate oxygen saturation.
- 4) Not intubated
- 5) Requiring:
 - (a) nasal continuous positive airway pressure (nCPAP), or
 - (b) high flow nasal cannula (≥ 2 L/kg/min) (HFNC), or
 - (c) non-invasive ventilation.

Cohort 2: RDS Patients Post Early Surfactant Instillation

- 1) NICU patient <24 hours of age.
- 2) Intubated, given instilled surfactant at \leq 1hours of age, then extubated within 6 hours.
- 3) Inspired oxygen \geq 25 and \leq 40 % to maintain adequate oxygen saturation.
- 4) Not intubated.
- 5) Requiring: (a) nasal continuous positive airway pressure (nCPAP),or
(b) high flow nasal cannula (\geq 2 L/kg/min) (HFNC), or
(c) non-invasive ventilation.
- 6) Increasing in FiO₂ and/or respiratory support for \geq 1 hour.

5.2 Exclusion criteria

- 1) Congenital anomaly limiting care options or requiring early surgery.
- 2) Cardiopulmonary decompensation.
 - a) hypotension with metabolic acidosis (base excess < -10 meq/l).
 - b) Oxygen saturations < 88% at start of aerosolization.
 - c) PaCO₂ \geq 60 mmHg at start of aerosolization.
- 3) Grade 3 or Grade 4 intraventricular hemorrhage by cranial ultrasound, if known.
- 4) Acute hypoxic encephalopathy with or without seizures.

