- 2) a subsequent deterioration in respiratory function, and
- 3) no adverse event during the initial dose.

Usual Care: There will be no protocol driven interventions in the usual care group. Use of pacifiers as tolerated in these patients is encouraged to decrease the incidence of loss of continuous airway pressure through the mouth.

Sham therapy has not been included because it cannot produce an effective masking of treatment assignment to care givers because of both the presence of residual Infasurf in the mouth and stomach and there is a reliable decrease in inspired oxygen requirement by the end of aerosolized Infasurf therapy.

Separation of the effect of additional gas infusion derived from aerosolized Infasurf effect by sham treatment is unnecessary. Pressure in the airway is set by the nasal therapy and that therapy will be adjusted, if necessary, to maintain the airway pressure ordered by the supervising provider. The tidal volume of spontaneous breathing participants is affected only by the airway pressure not by the volume of bias flow. Usual care patients will have the positive airway pressure set and adjusted as their respiratory status requires by their supervising provider.

The decision not include a sham procedure was also based on the concern of interrupting and/or modifying ongoing respiratory support in fragile newborns with RDS to implement the sham. Such an intervention has no reasonable expectation of benefit for the subject but does have some potential for adverse consequences. There will be no protocol driven interventions in the usual care group.

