15 APPENDICES

APPENDIX A

Intervention Notes Formats

Initial Aerosol Procedure Note

Date Time: Patient was randomized to the Aerosolization Group in the Aerosolized Infasurf Trial in the {never treated} {previously instilled} cohort. The initial aerosolization was started at ___:___ hours and was completed at ___:___ hours. A total of ___ mL of Infasurf was aerosolized. The Inspired O₂ prior to starting the aerosol was ___%. The aerosolization {was} {was not} completed. There {was no} {was an} adverse event during the aerosol delivery. {If present describe in detail}.

Repeat Aerosol Procedure Note

Date Time: A repeat aerosolization was started at ___:___ hours and was completed at ___:___ hours. A total of ___ mL of Infasurf was aerosolized. The Inspired O₂ prior to starting the aerosol was ___%. The aerosolization {was} {was not} completed. There {was no} {was an} adverse event during the aerosol delivery. {If present describe in detail}.

Usual Care Procedure Note

Date Time: Patient was randomized to the Usual Care Group in the Aerosolized Infasurf Trial in the {never treated} {previously instilled} cohort. The Inspired O₂ at the time of randomization was ___%.

Aerosolized Infasurf Trial Case Report

1. Identity Data

Last Name _____

Date of Birth ____/____/____

Time of Birth ____:____

Hospital # _____

Study # _____

Consent # _____

Strata A B

Rx Group Usual Care Aerosolized

2. Demographic Data

Sex M F

 Single MultA MultB MultC

Birth Wt _____grams

Gestational Age ____wks ____days

Maternal Steroids N <12 hrs >12 hrs

Delivery: Vaginal C-Section

APGAR ____ 1min ____ 5 min

Intubated in DR Y N

Surfactant in DR Y N

3 A. 1st Aerosolization Procedure Data

Date		
Start time		
End time		
Patient Age (hrs)		
Dose (mL)		
Aerosol duration (min)		
Mode of Support		
FiO2	Pre	
	30 min	
	60 min	
	90 min	
	120 min	
	180 min	
	240 min	
Aersolization interrupted		

3 B. 2nd Aerosolization Procedure Data

Date		
Start time		
End time		
Patient Age (hrs)		
Dose (mL)		
Aerosol duration (min)		
Mode of Support		
FiO2	Pre 1	
	30 min	
	60 min	
	90 min	
	120 mins	
	180 min	
	240 min	
Aersolization interrupted		
Full dose given		

3 C. 3rd Aerosolization Procedure Data

Date		
Start time		
End time		
Patient Age (hrs)		
Dose (mL)		
Aerosol duration (min)		
Mode of Support		
FiO2	Pre 1	
	30 min	
	60 min	
	90 min	
	120 mins	
	180 min	
	240 min	
Aersolization interrupted		
Full dose given		

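### Exclusion criteria 2b and 2c are timed after assignment, at a moment that only the aerosol arm reaches; intent-to-treat covers this by default, but the timing should be corrected and the exceptions closed

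*Combined protocol and SAP*

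**What the plan says.** Section 5.2 lists two exclusions under cardiopulmonary decompensation that are tied to the moment of dosing. Criterion 2b reads "Oxygen saturations < 88% at start of aerosolization". Criterion 2c sets a PaCO2 limit of "60 mmHg at start of aerosolization". The other exclusions carry no such time anchor.

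On assignment, section 4.8 says "Patient assignment will be to the study arm indicated by the next envelope in sequence opened after consent is obtained". On the control arm, section 6.1 says "There will be no protocol driven interventions in the usual care group".

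On the analysis set, section 9.1 says "Subjects will be randomized to the intervention or active control arm" and then "Subjects will be included in primary data analyses according to their randomized assignment irrespective of the treatment actually received", and labels this intent-to-treat. It names one kind of exception, withdrawal of consent to use data, in wording that does not claim to be a complete list. Elsewhere 9.1 allows all or part of an infant's data to be classed as non-evaluable before database lock. The rationale must be defined prospectively, but no criteria are given. The section also says that a SAP with further detail will be developed.

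**The concern.** An exclusion criterion normally decides who is randomized. These two can only be met by an infant who has already been randomized, and only by one assigned to aerosol. One part of the plan therefore calls such an infant excluded, while another says to analyse the infant as assigned.

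If the exclusion or the non-evaluable clause were allowed to prevail, infants would be lost from one arm only, in a trial where everyone knows the assignment. An infant who desaturates or retains CO2 before dosing may be more likely than average to need instilled surfactant. If so, removing such infants would lower the aerosol arm's event rate without any treatment effect, and the comparison would favour aerosol.

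**Working it through.** **Order of events.**
1. Consent is obtained, then the envelope is opened (4.8). The arm is now fixed.
2. In the aerosol arm, dosing starts at some later point, and 2b and 2c are judged there (5.2).
3. In usual care there is no dosing (6.1), so 2b and 2c have no time point.
4. Instillation is counted from randomization to 72 hours of age (7.2), so the outcome window is already open when 2b and 2c are judged.

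Read literally, the two criteria can apply to one arm only.

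**The plan's own figures (9.2).** For 60% versus 48%, one-sided 5% and 80% power, the continuity-corrected two-proportion formula gives 229 per group, as stated. Exact Fisher power at 229 is 80.2%, against the stated 80.1%. Without continuity correction, power at 229 is 82.6%. For the post-instilled cohort (200 infants, so 100 per arm; 60% versus 42%), power is 82.0% by pooled normal approximation and 78.6% by exact Fisher, against a stated figure of about 80%. The sample size is not in dispute.

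**Illustration if infants were dropped.** Inputs from the plan are 60% events in usual care, 229 or 100 per arm, and one-sided 5%. Assumed inputs, not in the documents, are the share x of the aerosol arm that is dropped and the share q of those dropped who are events. There is no true effect.

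- Aerosol rate among those left: p = (0.60 − xq)/(1 − x), with m = n(1 − x) infants.
- Spurious difference: d = 0.60 − p.
- Error = Φ[(d − 1.645 × SE0)/SE1], where SE0 is the pooled and SE1 the unpooled standard error.

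Worked case, n = 229, x = 0.05, q = 1.0: p = (0.60 − 0.05)/0.95 = 0.5789; d = 0.0211; m = 217.55; SE0 and SE1 are both 0.0466. Then (0.0211 − 1.645 × 0.0466)/0.0466 = −1.193, and Φ(−1.193) = 0.1165.

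| Share dropped, x | Infants of 229 | Error at 229 per arm, q = 80% to 100% | Error at 100 per arm, q = 80% to 100% |
|---|---|---|---|
| 1% | 2 to 3 | 5.5% to 6.0% | 5.3% to 5.6% |
| 2% | 4 to 5 | 6.0% to 7.1% | 5.6% to 6.3% |
| 5% | 11 to 12 | 7.8% to 11.6% | 6.7% to 8.9% |

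With q = 60% (average risk), the error is 5.0% in every cell. A simulation with a binomial number of infants dropped agreed to within 0.1 percentage point.

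**If they stay in, undosed.** The null error is unaffected. If a share f of the aerosol arm gets no benefit, its rate is 0.48(1 − f) + 0.60f. At 229 per arm, pooled normal power goes from 82.6% to 81.9% (f = 1%, rate 48.12%) or 79.1% (f = 5%, rate 48.6%). At 100 per arm it goes from 82.0% to 81.3% or 78.4%. Intent-to-treat already implies this loss.

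**The case against.** The strongest reply is that 9.1 already answers the question. An infant assigned to aerosol and not dosed is the ordinary case for intent-to-treat, and the only exception named is withdrawal of consent. Any exclusion needs a prospectively defined rationale, and evaluability criteria may appear in the SAP that 9.1 says will follow. Section 5.3 does not list meeting 2b or 2c as a reason for withdrawal. On this reading, bias would require the sponsor to depart from its own rule.

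Most of that stands. A reader might infer that the plan drops these infants, that nothing in it addresses them, or that the type I error is above 5%. The documents support none of these: no section prescribes dropping anyone, and the default is to keep them.

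A reader might also take Appendix A as confirming one-sided screening, because the usual-care note records inspired oxygen "at the time of randomization was" whereas the aerosol notes record it "prior to starting the aerosol was". That goes too far. Those notes hold neither saturation nor PaCO2, and the case report form collects respiratory support in both arms.

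The size is also open to challenge. Entrants are maintaining adequate saturation on 25% to 40% oxygen (5.1), and no blood gas is mandated (4.9), so 2c may often not be assessable. The indication for instillation in 7.2 rests on sustained oxygen need with positive pressure, not on PaCO2 or a single low saturation. An event rate of 80% to 100% among those dropped is therefore an assumption without support in the plan.

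What survives is narrower. The timing of 2b and 2c is a stated rule set at the wrong moment. The intent-to-treat sentence speaks of treatment received, not of infants whom the protocol itself calls excluded, and its exceptions are not closed.

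**Conclusion.** The point holds as a timing fault in 5.2 together with a gap in 9.1. As written, 2b and 2c can exclude only aerosol-assigned infants. Under the default in 9.1 they remain in the primary analysis and there is no bias; bias arises only if the exclusion criteria or the non-evaluable clause override that default.

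The share affected is unknown and may be near zero. Every error rate above 5% rests on assumed drop shares and assumed event rates, and should not be read as an estimate for this trial. Severity is minor to moderate: the harm is conditional, but the trial is pivotal and unblinded, and the ambiguity is easy to remove.

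**What to change.** - **Section 5.2:** judge 2b and 2c in every infant before the envelope is opened, on the latest charted values (PaCO2 if measured). This adds no testing, in keeping with 4.9.
- **Section 6.1:** keep the same limits at the start of the initial aerosol only as a reason to withhold or delay dosing. State that dosing may proceed on recovery, that the infant stays in the assigned arm and in data collection, and whether the limits also apply to re-doses, which are by definition given after deterioration.
- **Section 9.1:** state that withdrawal of consent to use data is the only exception to intent-to-treat, so that every other randomized infant with an observed 72-hour outcome is analysed as randomized, dosed or not. Missing outcomes are reported under 9.4, which rules out imputation.
- **Forms:** record pre-randomization saturation and PaCO2 (if measured) on a form completed for every randomized infant. The aerosol note will not serve, because 4.9 requires it only for infants who received aerosol.

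The cost is a few sentences, two form fields and a few infants screened out. If 1% to 5% are screened out (assumed), 658/0.99 = 665 to 658/0.95 = 693 infants are needed to randomize 658. At the projected 80 per month that is 8.3 to 8.7 months instead of 658/80 = 8.2, within the stated 365 days.
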